#### 3.1 Inclusion criteria

1. Patients with one to three (1–3) metachronous colorectal liver metastases, up to 5 cm in size, that are difficult to resect due to their position (likelihood of insufficient healthy liver after resection) or inaccessible for treatment with standard ablation techniques because they are located on large hepatic vascular structures (portal veins, hepatic veins or their inflow into the inferior vena cava, immediate vicinity of vena cava), but are otherwise operable.
2. Patients with up to three (3) recurring colorectal liver metastases, each with a maximum diameter not exceeding five (5) cm, and for which other treatment is either unacceptably risky due to possible insufficient residual liver volume after resection or expected to be less effective due to the proximity of veins in RFA.

*Patients in groups 1 and 2 are patients in whom standard treatment options (systemic and/or surgical) have been exhausted. ECT will be offered to these patients as the only therapeutic option. If a patient has a large number of metastases that are unresectable and at the same time unsuitable for RFA, the metastases will be treated with ECT, while any other metastases will be resected or treated with RFA.*

3. Patients with synchronous colorectal liver metastases, in whom—due to their poor general health or the extent of the disease—first the removal of the primary tumour is planned, and after 2–3 months, surgery on the metastases, with systemic treatment taking place in the meantime. ECT would be used to treat metastases up to 5 cm in maximum diameter during the first surgical procedure, i.e. when the primary tumour is removed.
4. Patients with bilateral metachronous colorectal liver metastases who require two-stage surgery due to the extent of the disease, i.e. right portal vein ligation and excision or RFA of metastases in the left hepatic lobe at the first stage and right hepatic lobe resection at the second stage. During the right portal vein ligation surgery, the metastases should be accessible in order to apply electroporation pulses without major manipulation and mobilization of the liver, so as not to create additional problems for the second planned procedure, i.e. the removal of metastases by resecting the right hepatic lobe.

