*Patients in groups 3 and 4 are potentially curable using standard treatment. The fact that these patients will be operated on twice as part of standard treatment will be used to apply ECT during the first procedure and to resect treated and untreated metastases during the second. The added ECT used on these patients will not affect the standard treatment recommended in the current guidelines.*

5. The patient is offered ECT treatment even if the patient refuses standard treatment options.
6. Histologically and/or cytologically confirmed colorectal cancer.
7. Age above 18.
8. Life expectancy over 3 months.
9. Performance status (PS)  $\geq 70$  according to Karnofsky PS or  $\geq 2$  according to WHO recommendations.
10. Depending on the type of active substance, 2–5 weeks have passed since the last treatment, if any.

11. The patient must understand the treatment process and any side effects.
12. The patient must be able to give consent to participate in a clinical trial ('informed consent').
13. Prior to inclusion in the study, the patient should be treated by a multidisciplinary gastrointestinal tumour team.

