## 6.3 ECT adverse effects will be recorded in line with the criteria of the National Cancer Institute (NCI)

An adverse effect is an undesirable and unexpected sign, symptom or disease, regardless of the cause, which develops or worsens during the study and which includes pathological clinical observations and deviations in the values of laboratory-measured parameters. The latter are considered a side effect only if they require additional treatment or result in premature withdrawal of the patient from the study.

We will record any side effects that occur during the study and up to 30 days after the end of treatment. If a serious adverse reaction occurs more than 30 days after the end of treatment, the principal investigator will decide whether the complication is study-related or not.

We will record the start and end time of any adverse effect, and the cause-and-effect relationship between the adverse effect and ECT, cancer or other diseases, as well as assessing the severity of the adverse effect and describing the actions that will need to be taken.

The causal relationship between the adverse effect and the ECT will be assessed as follows:

- Not related to the study.
- Probably not related to the study.
- Possibly related to the study.
- Probably related to the study.
- Certainly related to the study.

The severity of side effects will be assessed using the following grades:

- Grade 1 – mild
- Grade 2 – moderate
- Grade 3 – a difficult complication requiring medical care
- Grade 4 – a life-threatening condition requiring immediate medical assistance
- Grade 5 – death

If a serious adverse effect is recorded during the study, the principal investigator will notify the responsible person at the National Medical Ethics Committee of the Republic of Slovenia in writing within 24 hours. A serious adverse effect is a complication that results in the following:

- death,
- a life-threatening condition requiring immediate medical assistance,
- hospitalization or extended hospitalization,
- prolonged inability of the patient to perform any task that they were able to perform before the onset of the complication,
- any event or condition which endangers the life or health of the patient and which, according to a medical assessment, could lead to any of the serious complications referred to above.

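### The end of adverse-effect recording is undefined; on the more natural reading routine recording stops at D30, before the group 3 second operation, from which only histology is planned

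*Combined protocol and SAP*

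**What the plan says.** **Recording window (section 6.3).** "We will record any side effects that occur during the study and up to 30 days after the end of treatment". The section does not say when the study ends for a patient or what counts as the end of treatment.

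**Later serious events (section 6.3).** For a serious reaction beyond 30 days, "the principal investigator will decide whether the complication is study-related or not". Separately, "If a serious adverse effect is recorded during the study, the principal investigator will notify" the ethics committee within 24 hours. The definition of serious includes admission to hospital and a longer hospital stay.

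**Timing of the second operation (section 3.1).** For group 3, "first the removal of the primary tumour is planned, and after 2–3 months, surgery on the metastases"; ECT is given at the first procedure. For group 4 the plan is "right hepatic lobe resection at the second stage", with no interval.

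**What is asserted about these patients (section 3.1).** Groups 3 and 4 are described as potentially curable by standard treatment, and "The added ECT used on these patients will not affect the standard treatment recommended in the current guidelines". The group 4 criterion asks for easily reached metastases "so as not to create additional problems for the second planned procedure".

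**Follow-up (section 6.1).** Clinical examination is scheduled at D7, D30, D60, D90 and D120. From later surgery the plan lists histology of the removed metastases and no surgical outcome. Section 7 promises a descriptive account of adverse effects.

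**The concern.** Groups 3 and 4 would have two operations anyway, and the trial adds ECT to the first. The safety question specific to them is whether that addition delays, changes or complicates the second operation. If routine recording closes before that operation, its non-serious complications are not collected systematically. A delay or cancellation is not an adverse effect as section 6.3 defines one, so no window, long or short, would capture it. The trial could then report on safety in potentially curable patients without having looked at the event that matters most to them, although they are still attending visits at that time.

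**Working it through.** The documents give no figure of their own to reproduce here. The check is a timeline, a comparison of two readings, and a note on precision.

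**1. Inputs**
- Window: 30 days after the end of treatment (section 6.3).
- ECT: one bleomycin bolus, with pulses 8–28 minutes later (section 5.1). No repeat session is described. Assumption: end of treatment = ECT day = day 0.
- Second operation in group 3: 2–3 months after the first procedure (section 3.1).
- Visits after treatment: D7, D30, D60, D90, D120 (section 6.1).
- Conversion: 1 month = 30.44 days.

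**2. Timeline for group 3 under that assumption**

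| | 2 months | 3 months |
|---|---|---|
| Day of second operation | 2 × 30.44 = 60.9, about D61 | 3 × 30.44 = 91.3, about D91 |
| Gap after D30 | 60.9 − 30 = 30.9 days | 91.3 − 30 = 61.3 days |
| Operation + 30 days | 60.9 + 30 = 90.9, about D91 | 91.3 + 30 = 121.3, about D121 |

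Three of the five visits after treatment (D60, D90, D120) fall after D30. Group 4 cannot be placed, because no interval is stated. Groups 1 and 2 have no planned second operation.

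**3. Two readings of the window**
- *Narrow:* recording covers treatment and the following 30 days, and so ends at D30. The separate sentence on serious reactions after 30 days then has a clear job.
- *Broad:* the study lasts to the D120 visit, or treatment includes the second stage. The second operation is then largely or wholly covered for group 3. If the study runs to D120, however, the separate sentence on later serious reactions is largely redundant, because those events would already be recorded.

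The narrow reading fits the two sentences together better, but the text does not exclude the broad one.

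**4. What neither reading supplies**
Sections 6.1, 7 and 8 name no item for whether the second operation took place as planned, when it took place, or with what complications.

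**5. How much could be learned**
The extension has 15 patients; the number in groups 3 and 4 is not stated. For an assumed n of 5, 10 or 15 such patients:
- One-sided 95% upper bound after zero events, 1 − 0.05^(1/n): 45%, 26%, 18%.
- Chance of at least one event at an assumed true rate of 10%, 1 − 0.9^n: 41%, 65%, 79%.

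**The case against.** A reader might infer four stronger things that the documents do not support.

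- *Recording certainly stops at D30.* The sentence also covers the time during the study, and the definition of an adverse effect refers to the study period. The D30 cut-off depends on how two undefined terms are read.
- *The trial would report no second-operation problems by construction.* Major complications of a liver resection would often prolong the hospital stay and so count as serious, and section 6.3 provides for serious reactions after 30 days. Examination at D60, D90 and D120 and histology of the resected tissue add partial information.
- *Late serious events count only at the principal investigator's discretion.* The rule is about attribution. What it leaves unsaid is that every such event is recorded, graded and reported whichever way attribution goes.
- *All two-stage patients are operated on at about D61–D91.* That interval belongs to group 3 alone.

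It can also be argued that the statement on standard treatment describes an unchanged treatment plan and is not a hypothesis about surgical outcome, that the phrase about the second procedure is a precaution built into eligibility, and that a longer window in a small study without a comparator could not verify the statement anyway. These arguments have weight: they limit the claim to a missing description. They do not remove the gap, because the plan already undertakes to describe adverse effects, and delay or cancellation is not captured on any reading.

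**Conclusion.** The point holds in a limited form. The end of recording is ambiguous. On the more natural reading, routine recording of non-serious events closes about 31–61 days before the group 3 second operation, although patients are seen until D120. This rests on a single ECT session marking the end of treatment. On the broad reading the timing gap largely disappears for group 3, but the absence of any second-operation outcome other than histology remains. The statement that ECT leaves standard treatment unaffected therefore has no systematic check in groups 3 and 4. This does not invalidate the trial. It is a worthwhile, inexpensive improvement to what the trial can say about safety in potentially curable patients, and with an upper bound of 18% or more even after no events in 15 patients, it would allow description only.

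**What to change.** Amend section 6.3 and the case-report form as follows.

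1. Define the end of treatment and the end of the study for recording purposes.
2. State that all adverse effects, serious or not, are recorded, graded and attributed on the existing five-level scale through D120 and, in groups 3 and 4, through 30 days after the second operation.
3. State that every late serious event is recorded first and attributed afterwards.
4. For groups 3 and 4, collect and report descriptively whether the second operation was done as planned, any delay in days, and its complications. Give the number of patients in these groups as the denominator.

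Cost: a wording amendment, a few form fields, slightly more data entry and a longer adverse-effect list. For group 3 the extended window ends at about D91–D121, so the existing D60, D90 and D120 visits cover nearly all of it. Some patients may need a short follow-up contact beyond D120. For group 4 the need cannot be estimated until an expected interval is stated.

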## 5 TREATMENT: ELECTROCHEMOTHERAPY (ECT)

Patients with multiple bilateral metastases scheduled for two-stage surgery depending on their general condition and extent of the disease will have their right portal vein ligated and up to 3 metastases treated on the right hepatic lobe with up to 3 cm in maximum diameter using ECT during the first surgical procedure. On the left, metastases will be treated using established methods, such as surgery and RFA. During the second procedure, the entire right half of the liver will be removed.

In patients with liver metastases in areas where, due to the proximity of the main hepatic veins, surgery is not possible and the success of other ablation techniques cannot be predicted, ECT will be performed.

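### The causality scale in Section 6.3 asks about ECT but grades relation to the study, and it gives no place to surgery or same-session procedures, so ECT toxicity cannot be reliably separated from operative toxicity

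*Combined protocol and SAP*

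**What the plan says.** Section 6.3 collects events whatever their origin: "An adverse effect is an undesirable and unexpected sign, symptom or disease, regardless of the cause". For each event it plans to record "the cause-and-effect relationship between the adverse effect and ECT, cancer or other diseases". The five-level scale is introduced with "The causal relationship between the adverse effect and the ECT will be assessed as follows", and its answers run upward from "Not related to the study" through "Possibly related to the study" to certain relation. All five name the study; none names ECT.

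ECT is given during an operation that often includes other procedures. In group 3 of Section 3.1, "ECT would be used to treat metastases up to 5 cm in maximum diameter during the first surgical procedure", which is the operation that removes the primary tumour. Section 5 says that the two-stage patients "will have their right portal vein ligated and up to 3 metastases treated on the right hepatic lobe", with surgery or RFA on the left side. For groups 1 and 2, when there are many metastases unsuited to resection and RFA, Section 3.1 says "the metastases will be treated with ECT, while any other metastases will be resected or treated with RFA".

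Section 6 makes the recording of adverse effects of ECT one of three levels of follow-up. Section 7 lists adverse effects among the results to be described.

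**The concern.** There are two defects, and they compound each other. First, the question and the answers of the scale refer to different things. ECT means the drug plus the pulses; the study may also be taken to include an operation done in order to deliver them. Second, the list of causes omits the most obvious competitor for an event in the days after surgery, which is the surgery itself with its anaesthesia and accompanying procedures.

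What is at stake is the safety description of ECT. Without a comparison arm for adverse effects, the investigator's attribution is the only means of separating the effect of ECT from that of the operation. If the grade can be understood in two ways and the competing cause is not recorded, a table of related events depends partly on how each investigator read the form and on which procedures accompanied ECT.

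**Working it through.** No arithmetic in the plan bears on this, so the check sets the passages side by side.

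**Step 1: question against answers (Section 6.3).** The introduction asks about ECT; the five answers refer to the study. The rule for serious reactions later than 30 days after treatment also asks about relation to the study. No sentence equates the two terms.

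**Step 2: listed causes against what happens in the session.** The listed causes are ECT, cancer and other diseases.

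| Entry group (Section 3.1) | Procedures in the ECT session | Standing of the operation | On the list of causes? |
|---|---|---|---|
| 1 and 2 | ECT; resection or RFA of other metastases in some patients | ECT is offered because standard options are exhausted | ECT only |
| 3 | ECT; removal of the primary tumour | Part of standard treatment, ECT added | ECT only |
| 4 | ECT; right portal vein ligation; excision or RFA on the left (also Section 5) | Part of standard treatment, ECT added | ECT only |

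Anaesthesia is common to all rows and is not listed. Systemic therapy is not listed either, although it is planned between the two operations in group 3, and Section 3.1 allows entry 2–5 weeks after earlier treatment.

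**Step 3: do the two readings give different grades?** Take a complication that the investigator believes arose from the operation and not from the drug or the pulses.

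- Read as relation to ECT, it belongs at the unrelated end in every group.
- Read as relation to the study, it belongs at the unrelated end in groups 3 and 4, because the operation is part of standard treatment. In groups 1 and 2 it could be graded as related where the operation was done to deliver ECT.

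So for such an event the readings agree in groups 3 and 4 and can part in groups 1 and 2. The missing operative cause matters in every group: for a bleed that could come from an electrode track or from a concurrent procedure, the investigator can choose a middle grade, but no rating shows that the operation was the rival explanation.

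**Step 4: is there another way to separate the two?** Section 2, under pulse synchronization, already attributes some cardiac changes at least partly to medication and postoperative pain, and calls for surgical controls. Section 6.2 provides 10–15 of them, for ECG recordings only. Section 7 gives no rule for relatedness, and Section 8 does not mention adverse effects.

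**Step 5: size.** The documents state no adverse-effect rates, so the number of misattributed events cannot be derived. Only the coarseness of the result can be shown. Section 1 adds 15 patients, so one patient reclassified moves a proportion by 1/15 = 6.7 percentage points.

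**The case against.** The strongest reply is that the introductory sentence settles the meaning: the investigator is asked about ECT and will answer about ECT, and the wording of the options is a slip. A surgical complication can be graded as unrelated in any group. The three named causes are not declared to be a closed list, and the case report form is not among the documents. The analysis is descriptive, with no threshold or test on related events. Serious events are notified within 24 hours whatever their cause, and the stated purpose of the extension is efficacy.

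Much of this stands and limits the point. A reader might infer that ECT toxicity cannot be read from the form at all, or that every surgical complication must be charged to ECT, cancer or another disease. The documents do not support either inference: an ECT-relatedness grade is collected, and the unrelated grades are available. A reader might also infer that the entry group dictates the grade. The text permits that outcome but does not prescribe it, and it disappears if the introductory sentence is followed.

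The reply does not remove the contradiction on the page. It also does not supply a field for the operation, or a surgical comparison for anything other than ECG. A descriptive result still needs a category with one meaning.

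**Conclusion.** The point holds in a limited form. Section 6.3 specifies an instrument whose question and answers disagree and whose named causes omit surgery, anaesthesia and concurrent procedures. The accompanying procedures differ by entry group, and the surgical controls cover ECG alone. ECT toxicity therefore cannot be reliably separated from operative toxicity in the adverse-effect results. This is more than a missing detail, because the instrument is stated and is inconsistent.

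The conclusion rests on the form following the text of Section 6.3. It does not rest on the operation being open, which the documents do not say, nor on every patient in groups 1 and 2 having resection or RFA, which is conditional. Whether systemic therapy in group 3 falls inside the 30-day recording window cannot be settled from the text. No percentage of misattributed events is claimed, and the direction of any error is not known.

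**What to change.** In Section 6.3:

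1. Word all five answers as relation to ECT, defined as bleomycin and electroporation together.
2. Add a second rating on the same five levels for relation to the operation, anaesthesia and concurrent procedures (primary tumour removal, portal vein ligation, resection, RFA).
3. Add surgery and systemic therapy to the list of causes.

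In Section 7, tabulate ECT-related events separately for entry groups 1–2 and 3–4. State in advance where a patient belongs who enters because of refusing standard treatment (criterion 5 of Section 3.1).

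Rating bleomycin and electroporation separately is optional: Section 2 defines ECT as the combination, so reporting its toxicity does not require the split.

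The cost is a few more fields on the adverse-effect form and one table. Some events will be rated as possible for more than one cause; that is a fair record of the uncertainty, but the table must show it. The change should be made before events are recorded, because attribution is hard to reconstruct afterwards.

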## **7 DATA PROCESSING**

The results of the proposed clinical trial will be analyzed descriptively by describing the antitumour effect, any adverse effects and the patients' quality of life after treatment of colorectal liver metastases using ECT.

## **8 STATISTICAL ANALYSIS**

All data will be entered into a Microsoft Access 2010 database, which will be used for all calculations except for statistical analysis, which will be performed with GraphPad Software (La Jolla, CA, USA). The log-rank (Mantel-Cox) test will be performed on the Kaplan-Meier estimates. A chi-squared test will

be used for the statistical comparison of response according to tumor location. A two-tailed P value less than 0.05 will be considered to be statistically significant.

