A phase I/II clinical study is currently underway at Institute of Oncology Ljubljana to assess the safety and efficacy of treatment for colorectal liver metastases using ECT. We wish to include an additional fifteen (15) patients within phase II using this protocol. To date, 17 patients have been included in the clinical study, and preliminary results in 16 of these patients indicate that treating colorectal liver metastases and one HCC patient using ECT is a safe method for treating tumours even in hard-to-reach locations. Preliminary MRI results in all patients testify to radiological changes similar to those observed after RFA treatment. The response to ECT treatment was complete in 50% of patients and partial in the remaining 50% of patients. Preliminary histological analysis results for all ECT-treated metastases after surgical removal indicate progressive degenerative changes within metastases and a statistically significant reduction in viable tumour tissue in ECT-treated metastases compared to non-ECT-treated metastases ( $p < 0.001$ ). We were the first to publish the technological part of the procedure in the clinical case.

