### 6.1. Effects of treating colorectal liver metastases using ECT

- Early treatment effects will be assessed using DCE-US or CT based on changes in tumour blood flow after ECT compared to pre-ECT blood flow.
- Late effects will be assessed based on modified RECIST criteria, taking into account the change in the size and density of treated tumour nodules before and after ECT. These will be assessed based on DCE-MRI images; the volume of the metastases will be calculated using the formula  $V = \frac{a \times b^2 \times \pi}{6}$ , where a is the shorter and b the longer metastasis diameter.

Based on the assessment of the late ECT effects, the response to treatment will be evaluated in line with the WHO classification:

- Complete response (CR): complete disappearance of the tumour nodule
  - Partial response (PR): reduction of tumour nodule size by more than 50%
  - No change (NC): decrease in tumour nodule size by less than 50% or increase in tumour nodule size by less than 25%
  - Progressive disease (PD): growth of the tumour nodule by more than 25%
- The direct effect will be assessed by histological analysis of those metastases that will be surgically removed.
  - EORTC Quality of Life questionnaire according to QLQ C30 standards

EXAMINATION/TEST	Screening period until D -14	D -1	D 7	D 30	D 60	D 90	D 120
clinical examination, anamnesis	X	X	X	X	X	X	X
ECG	X	X					

DCE-MRI	X			X		X
DCE-US	X			X	X	X
CT perfusion	X			X		X
Blood count	X	X	X			
Coagulation tests	X	X	X			
Biochemical blood analysis	X	X	X	X	X	X
EORTC QLQ C30 questionnaire	X		X	X		

\*D = day

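### The chi-squared test of response by tumour location makes no allowance for several nodules from one patient, so if it is run on nodules its 5% level is not assured

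*Combined protocol and SAP*

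**What the plan says.** Section 8 gives one sentence to this analysis: a chi-squared test will "be used for the statistical comparison of response according to tumor location". It then sets the threshold: "A two-tailed P value less than 0.05 will be considered to be statistically significant". It names no unit of analysis, no location classes, no choice of continuity correction and no method for several nodules in one patient.

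Section 6.1 defines all four response categories on the nodule, for example "Complete response (CR): complete disappearance of the tumour nodule". Section 2 (Treatment of liver tumours) reports the preliminary result on a different unit: "The response to ECT treatment was complete in 50% of patients and partial in the remaining 50% of patients".

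On the number of nodules, section 3.1 admits "Patients with one to three (1–3) metachronous colorectal liver metastases, up to 5 cm in size" (group 1) and "Patients with up to three (3) recurring colorectal liver metastases" (group 2). Section 5 has "up to 3 metastases treated on the right hepatic lobe" in the two-stage surgery patients. Group 3 carries no stated limit on number, and section 3.1 also foresees an open-ended case: "If a patient has a large number of metastases that are unresectable and at the same time unsuitable for RFA".

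**The concern.** Response as the plan defines it, and location, are both properties of a nodule. Sections 2, 4 and 5.2.2 describe depth, size and nearness to vessels for the metastasis, not for the patient. The literal reading of the test is therefore a table of nodules by location and response. Nodules from one patient share a host, a tumour biology and one intravenous bleomycin dose (section 5.1), so their responses may be correlated. Pearson's chi-squared test assumes independent observations. If correlated nodules also tend to share a location, the test overstates the information in the table and rejects too often.

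Nearness to large vessels is one of the reasons for offering electrochemotherapy in groups 1 and 2. A false difference by location could therefore influence later views on which lesions suit the method.

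**Working it through.** **Inputs from the documents.** Two-tailed 0.05 (section 8). 15 new patients (section 1) and 17 already included (section 2), so 15, or 17 + 15 = 32 if both parts are pooled. Pooling is not stated, so both sizes were run. Up to three treated nodules per patient (sections 3.1 and 5). Complete response probability 0.5 under the null (section 2).

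**Assumptions, because the documents give no values.** Two location classes; response ICC 0.3 and 0.5; three distributions of nodules per patient (three each; equal thirds with 1, 2 and 3; 60/25/15% with 1, 2 and 3); four patterns of location within a patient.

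**Step 1: the plan's own figure.** With independent observations, 2 × (1 − Φ(1.960)) = 0.050. Simulation with one nodule per patient gives 0.042–0.047 (15 patients) and 0.048–0.053 (32 patients) without continuity correction. The stated level is reproduced when each patient supplies one observation.

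**Step 2: formula for fully shared location.** The design effect is DE = 1 + (Σm²/Σm − 1) × ICC, where m is the number of nodules per patient. The actual level is 2 × (1 − Φ(1.960/√DE)).

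- Three each: Σm²/Σm = 3. ICC 0.3: DE = 1.60, level 0.121. ICC 0.5: DE = 2.00, level 0.166.
- Equal thirds: Σm²/Σm = 14/6 = 2.33. ICC 0.3: DE = 1.40, level 0.098. ICC 0.5: DE = 1.67, level 0.129.
- 60/25/15%: Σm²/Σm = 2.95/1.55 = 1.90. ICC 0.3: DE = 1.27, level 0.082. ICC 0.5: DE = 1.45, level 0.104.

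The level reaches 10% when DE = (1.960/1.645)² = 1.42. That needs an ICC of 0.21 with three each, about 0.31 with equal thirds and about 0.46 with the 60/25/15% mix.

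**Step 3: simulation, no continuity correction.** 20,000 runs per cell. Each entry spans 15 and 32 patients. Partly shared means a within-patient location correlation of 0.5.

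| Nodules per patient | Shared, ICC 0.3 | Shared, ICC 0.5 | Partly shared, ICC 0.3 | Partly shared, ICC 0.5 | Unrelated, ICC 0.3–0.5 | Alternating, ICC 0.3–0.5 |
|---|---|---|---|---|---|---|
| Three each | 0.123–0.130 | 0.170 | 0.084–0.088 | 0.114–0.117 | 0.049–0.053 | 0.016–0.030 |
| Equal thirds | 0.099–0.104 | 0.134 | 0.076–0.077 | 0.094–0.097 | 0.050–0.053 | 0.018–0.033 |
| 60/25/15% | 0.085–0.088 | 0.103–0.110 | 0.068–0.070 | 0.079–0.081 | 0.050–0.055 | 0.025–0.040 |

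Simulation and formula agree for shared location. Raising the number of patients from 15 to 32 does not cure the problem, because the inflation depends on nodules per patient and the correlations.

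**Step 4: Yates correction.** With shared location and ICC 0.5 the level is 0.120–0.133 (three each), 0.072–0.089 (equal thirds) and 0.043–0.063 (60/25/15%). The correction compensates by being conservative: with one nodule per patient and independent data the level is only about 0.01 to 0.02.

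**The case against.** The strongest reply is that section 8 never says nodules are the unit, and the only response result in the documents is per patient. With one row per patient the level is close to 5%. This stands as far as it goes: a nodule-level test is an inference from section 6.1, not stated text. But a patient-level table would need a rule for a patient whose nodules lie in different places or respond differently, and the plan has none.

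Second, a reader might infer that the true error rate is double the nominal one or worse. The documents do not support that as a general statement. It needs a moderate to high ICC and a location largely shared within patients. Where location varies freely between nodules there is almost no inflation, and alternating locations make the test conservative, so even the direction is not fixed. Some sharing is plausible, because section 5 places the treated nodules of two-stage patients in the right lobe, but its extent is unknown.

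Third, the counts in section 3.1 are metastases at entry. Some may be resected or treated with RFA, so three treated nodules each is an upper case for groups 1 and 2.

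Fourth, section 7 calls the analysis descriptive, and no sample size or decision rule rests on this test. That limits the severity. It does not remove the point, because section 8 names a test and a significance threshold. Nor is this the plan's only efficacy comparison, as a reader might suppose: section 8 also lists a log-rank test.

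**Conclusion.** The concern holds in a conditional form. Applied to nodules, as the response definition in section 6.1 suggests, the named test ignores within-patient correlation, and the plan does not settle the unit. For response ICCs of 0.3 to 0.5 without continuity correction, the type I error is about 9–17% with shared location, 7–12% with partly shared location and 5–6% with unrelated location. It drops to roughly 2–4% when locations alternate. These figures rest on assumed ICCs, nodule counts and location agreement. What is firm is that the plan does not secure its 5% level; what is not known is by how much, or in which direction, it would miss.

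A reader might also take nearness to vessels as the sole reason for the treatment and so rank this higher. Section 3.1 gives other routes: insufficient remaining liver, the planned two-operation groups, and refusal of standard treatment. Location itself is undefined in section 8. This is a secondary comparison that should be fixed; the study's overall efficacy aim does not depend on it.

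**What to change.** Amend section 8 to:

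1. name the treated nodule as the unit for response by location;
2. prespecify the location classes and one binary response, for example complete response or not;
3. replace the chi-squared test with one patient-clustered method, chosen in advance: for example, a permutation test that keeps each patient's nodules together, or logistic GEE with the patient as cluster and a small-sample correction;
4. report the difference between locations with a patient-clustered 95% confidence interval, and give patient-level response beside it so that the result can be set against the preliminary one.

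The cost is a few sentences of plan text, intervals that will be somewhat wider where nodules share a location, and possibly software beyond GraphPad for this one analysis. No extra patients, visits or data are needed, provided the patient, location and response of every treated nodule are recorded. The error rate of the replacement was not simulated here; with about 15 patients the small-sample correction matters if GEE is chosen.
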